1. OVERALL PROTOCOL SUMMARY

1.1 Synopsis

Rationale for Proposed Clinical Study

A novel coronavirus designated severe acute respiratory syndrome coronavirus 2 (SARS-CoV-2) was first identified in December 2019 in Wuhan, China, and has since spread globally, resulting in an ongoing pandemic of Coronavirus Disease 2019 (COVID-19). Currently, remdesivir is available under emergency use authorization, but even with this antiviral the mortality of a hospitalized population with COVID-19 remains high. Multiple putative therapeutics involving repurposed agents (licensed or in late development) have been proposed, but there is no way to evaluate many of these agents due to lack of suitable animal models. An adaptive platform trial is one approach to allow for accelerated testing and selection of promising therapeutic agents in order to meet ongoing public health needs.

Study Design

This is a platform trial to conduct a series of randomized, double-blind, placebo-controlled trials using common assessments and endpoints in hospitalized adults diagnosed with COVID-19. BET is a proof-of-concept study with the intent of identifying promising treatments to enter a more definitive study (Adaptive COVID-19 Treatment Trial [ACTT], Accelerating COVID-19 Therapeutic Interventions and Vaccines [ACTIV], industry sponsored, or other). The study will be conducted at up to approximately 20 sites throughout the US. The study will compare different investigational therapeutic agents to a common control arm and determine which have relatively large effects. In order to maintain the double blind, each intervention will have a matched placebo. However, the control arm will be shared between interventions and may include participants receiving the matched placebo for a different intervention.

The goal is not to determine clear statistical significance for an intervention, but rather to determine which products have clinical data suggestive of efficacy and should be moved quickly into larger studies. Estimates produced from BET will provide an improved basis for designing the larger trial, in terms of sample size and endpoint selection. Products with little indication of efficacy will be dropped on the basis of interim evaluations. In addition, some interventions may be discontinued on the basis of interim futility or efficacy analyses.

One or more interventions may be started at any time. The number of interventions enrolling are programmatic decisions and will be based on the number of sites and the pace of enrollment. At the time of enrollment, subjects will be randomized to receive any one of the active arms they are eligible for or placebo. Approximately 100 subjects will be assigned to each arm entering the platform. A given site will generally have no more than 3 interventions at once.

Subjects will be assessed daily while hospitalized. See [Section 1.3 Schedule of Assessments](#) for details. The schedule is similar to ACTT to allow evaluation of endpoints used in the larger study. Once subjects are discharged from the hospital, they will have a study visit on Days 15, 22, and 29 as an outpatient, and these may be conducted by phone. Infection control considerations and other restrictions may limit the ability to have these visits in person.

All subjects will undergo a series of efficacy and safety laboratory assessments. Safety laboratory tests, blood (serum and plasma) research samples and oropharyngeal (OP) swabs will be obtained on Day 1 (prior to study product administration) and Days 3, 5, 8, and 11 while hospitalized. OP swabs (oropharyngeal swabs are preferred, but if these are not obtainable, saliva or nasopharyngeal or nasal swabs may be substituted) and blood research samples plus safety laboratory tests will be collected on Day 15 and 29 if the subject attends an in-person visit or is still hospitalized. However, if infection control considerations or other restrictions prevent the subject from returning to the clinic, Day 15 and 29 visits may be conducted by phone and only clinical data will be obtained. The Day 22 visit does not have laboratory tests or collection of samples and may also be conducted by phone. See Schedule of Assessments in Appendices for stage-specific details.

Table 1. Study Objectives*

OBJECTIVES	ENDPOINTS (OUTCOME MEASURES)
Primary	
To evaluate the clinical efficacy of different investigational therapeutics relative to the control arm in adults hospitalized with COVID-19 according to clinical status (8-point ordinal scale) at Day 8.	1. Not hospitalized, no limitations on activities; 2. Not hospitalized, limitation on activities and/or requiring home oxygen; 3. Hospitalized, not requiring supplemental oxygen - no longer requires ongoing medical care; 4. Hospitalized, not requiring supplemental oxygen - requiring ongoing medical care (COVID-19 related or otherwise); 5. Hospitalized, requiring supplemental oxygen; 6. Hospitalized, on non-invasive ventilation or high-flow oxygen devices; 7. Hospitalized, on invasive mechanical ventilation or extracorporeal membrane oxygenation (ECMO); 8. Death.
Key Secondary[†]	
To evaluate the clinical efficacy, as assessed by time to recovery, of different investigational therapeutics as compared to the control arm.	Day of recovery is defined as the first day on which the subject satisfies 1 of the following 3 categories from the ordinal scale: 
 • Not hospitalized, no limitations on activities; • Not hospitalized, limitation on activities and/or requiring home oxygen;

	
 Hospitalized, not requiring supplemental oxygen - no longer requires ongoing medical care.
Other Secondary[†]	

1. To evaluate the clinical efficacy of different investigational therapeutics as compared to the control arm as assessed by:
 
 Clinical Severity 
 Ordinal scale: 
 Time to an improvement of 1 category and 2 categories from Day 1 (baseline) using an ordinal scale. Mean change in the ordinal scale from Day 1 to Days 3, 5, 8, 11, 15, 22, and 29. 	
 Clinical outcome assessed using ordinal scale daily while hospitalized and on Days 15, 22, and 29.

 National Early Warning Score (NEWS): 
 Time to discharge or to a NEWS of ≤ 2 and maintained for 24 hours, whichever occurs first. Change from Day 1 to Days 3, 5, 8, 11, 15, and 29 in NEWS. 	
 NEWS assessed daily while hospitalized and on Days 15 and 29.

 Oxygenation: 
 Oxygenation use up to Day 29. Incidence and duration of new oxygen use during the study. Oxygen requirement. 	
 Days of supplemental oxygen (if applicable) up to Day 29. Supplemental oxygen concentration or flow rate.

 Non-invasive ventilation/high-flow oxygen: 
 Non-invasive ventilation/high-flow oxygen use up to Day 29. Incidence and duration of new non-invasive ventilation or high-flow oxygen use during the study. 	
 Days of non-invasive ventilation/high-flow oxygen (if applicable) up to Day 29.

 Invasive Mechanical Ventilation/extracorporeal membrane oxygenation (ECMO): 
 Ventilator/ECMO use up to Day 29. Incidence and duration of new mechanical ventilation or ECMO use during the study. 	
 Days of invasive mechanical ventilation/ECMO (if applicable) up to Day 29.

 Hospitalization: 	

 ○ Duration of hospitalization (days). 	
 ● Days of hospitalization up to Day 29.

 ● Mortality: 
 ○ 14-day mortality. ○ 29-day mortality. ○ Time to death up to Day 29. 	
 ● Date and cause of death (if applicable).

 ● Markers of inflammation and coagulation. 	
C-reactive protein (CRP), ferritin, d-dimer, fibrinogen, and troponin on Day 1; Days 3, 5, 8, and 11 (while hospitalized); and Days 15 and 29 (if attends in-person visit or still hospitalized).


2. To evaluate the safety of different investigational therapeutics as compared to the control arm as assessed by:
 
 ● Cumulative incidence of SAEs through Day 29. ● Cumulative incidence of Grade 3 and 4 clinical and/or laboratory adverse events (AEs) through Day 29. ● Discontinuation or temporary suspension of study product administration (for any reason). ● Changes in white blood cell (WBC) count with differential, hemoglobin, platelets, creatinine, total bilirubin, alanine aminotransferase (ALT), aspartate aminotransferase (AST), and international normalized ratio (INR) over time (analysis of lab values in addition to AEs noted above). 	
 ● Serious adverse events (SAEs). ● Grade 3 and 4 AEs. ● Episodes of early discontinuation or interruption of study product administration. ● WBC with differential, hemoglobin, platelets, creatinine, total bilirubin, ALT, AST, and INR on Day 1; Days 3, 5, 8, and 11 (while hospitalized); and Days 15 and 29 (if attends in-person visit or still hospitalized).
Exploratory	

1. To evaluate the virologic efficacy of different investigational therapeutics as compared to the control arm as assessed by:
 
 ● Percent of subjects with SARS-CoV-2 detectable in saliva (or best technology) sample at Days 3, 5, 8, 11, 15, and 29. ● Quantitative SARS-CoV-2 virus in saliva (or best technology) sample at Days 3, 5, 8, 11, 15, and 29. ● Quantitative SARS-CoV-2 virus in blood at Days 3, 5, 8, and 11. 	
 ● Qualitative and quantitative polymerase chain reaction (PCR) for SARS-CoV-2 in OP swab on Day 1; Days 3, 5, 8, and 11 (while hospitalized); and Days 15 and 29 (if attends in-person visit or still hospitalized). ● Qualitative and quantitative PCR for SARS-CoV-2 in blood on Day 1; Days 3, 5, 8, and 11 (while hospitalized).

2. To evaluate the impact of study interventions on markers of inflammation and immune response.
	
 ● Proteomic analysis of plasma cytokines and markers of inflammation. ● Transcription, epigenetic, and molecular profiles of mRNA in peripheral blood mononuclear cells (PBMC). ● Phenotypic and responsiveness markers in PBMC.

3. To evaluate post-baseline usage of key concomitant COVID-19 treatments (e.g., steroids) in investigational therapeutic arms as compared to the control arm.
	
 ● Type, dose, study day onset, and duration.

4. To evaluate standard of care steroid usage for indications other than COVID-19 post-baseline.
	
 ● Indication (ICD-10 code). ● Steroid type, dose, study day onset, and duration.

**Additional objectives and endpoints are listed in each stage-specific Appendix.*

†Each stage-specific Appendix may designate a different “Key Secondary” and additional “Other Secondary” objective(s)/endpoint(s) if appropriate for the specific intervention being evaluated.

Study Population

This trial will study putative therapeutics in a hospitalized adult population (≥ 18 years old) with COVID-19. The platform trial will have common inclusion criteria but may be modified for each stage for the unique risk of the study product in that stage. Exclusion criteria are described in each stage-specific appendix.

Inclusion Criteria:

1. Admitted to a hospital with symptoms suggestive of COVID-19 and requires ongoing medical care.
2. Subject (or legally authorized representative) provides informed consent prior to initiation of any study procedures.
3. Subject (or legally authorized representative) understands and agrees to comply with planned study procedures.
4. Male or non-pregnant female adult ≥ 18 years of age at time of enrollment.
5. Has laboratory-confirmed SARS-CoV-2 infection as determined by PCR or other commercial or public health assay in any specimen, as documented by either of the following:
 - PCR positive in sample collected < 72 hours prior to randomization; OR
 - PCR positive in sample collected ≥ 72 hours but < 7 days prior to randomization AND nonimproving or progressive disease suggestive of ongoing SARS-CoV-2 infection.

Note: if written documentation of the positive test result is not available at the time of enrollment (e.g., report came from other institution), the subject may be enrolled but the PCR should be repeated at the time of enrollment.

6. Illness of any duration, and at least one of the following:
 - Radiographic infiltrates by imaging (chest x-ray, computed tomography [CT] scan, etc.), OR
 - Blood oxygen saturation (SpO₂) ≤ 94% on room air, OR
 - Requiring supplemental oxygen, OR
 - Requiring mechanical ventilation or ECMO.
7. Women of childbearing potential must agree to either abstinence or use at least one primary form of contraception not including hormonal contraception from the time of screening through Day 29.
8. Agrees to not participate in another clinical trial (both pharmacologic and other types of interventions) for the treatment of COVID-19 through Day 29.

Exclusion Criteria:

Exclusion criteria are described in each stage-specific appendix.

Study Phase

Phase 2.

Study Sites

There will be up to approximately 20 sites throughout the US. Site selection will be determined as information becomes available about the epidemiology of COVID-19. Multiple sites will be IRB approved, but site activation will be dependent on the incidence of COVID-19 at the site.

Study Intervention

Each stage-specific appendix will detail the stage-specific study intervention.

Study Duration

The full adaptive study will last for up to 3 years.

Participant Duration

An individual subject will complete the study in about 29 days, from screening at Day -1 or 1 to follow-up on Day 29 ± 3 days.

Safety

- Given the potential severity of COVID-19 and limited information about the expected clinical course, there are no pre-specified study stopping rules.
- The Data and Safety Monitoring Board (DSMB) will have access to safety data electronically in real time.

Statistical Considerations

BET is a proof-of-concept study with the intent of identifying promising treatments that warrant future studies rather than declaring definitive efficacy after this study. The trial will enroll 100 patients per intervention and this will be compared with 100 control patients. Futility and early efficacy will be assessed after approximately 50 patients have been enrolled in the treatment and

control arms. The interim analysis will find an intervention futile if its point estimate for the primary endpoint has an odds ratio <1. An intervention can be declared efficacious early after 50 patients per arm have completed the study if the two-sided p-value is <.001. If the intervention continues to 100 patients, it will be declared promising if the final p-value is <.20 and will be considered as statistically significant if the final p-value is <.05.

Table 2 provides the probability to detect futility or efficacy given various odds ratios at interim and final analysis based on simulations (with 10,000 replications). An intervention with no effect (an odds ratio of 1) has a 50% chance of stopping at the interim analysis and has only a 10% chance to show promise. An intervention with an odds ratio of 2 has high power to show promise; that is, there is 91% probability that the final p-value will be <0.20 and only a 3% chance it will be stopped at an interim futility test.

Table 2. Simulated early stopping probabilities at the interim review (n=50/arm), and power calculations for the final study size (n=100/arm) for Day 8 Ordinal Score

OR	Probability of stopping for futility or efficacy at interim analysis for a given true odds ratio		Power at full study enrollment (100 treatment, 100 control)	
	Futility	Efficacy	Efficacy w/ alpha=0.05	Efficacy w/ alpha=0.20
0.75	0.793	0.000	0.001	0.008
1.00	0.502	0.000	0.026	0.096
1.25	0.260	0.004	0.136	0.329
1.50	0.126	0.014	0.348	0.604
1.75	0.060	0.036	0.581	0.802
2.00	0.028	0.070	0.765	0.913
2.25	0.013	0.119	0.879	0.961
2.50	0.006	0.179	0.939	0.984

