³ Baseline assessments should be performed prior to first study product administration. Laboratory tests performed as part of routine clinical care in the 24 hours prior to first dose will be accepted for the baseline laboratory tests. Baseline may be the same as the screening laboratory tests if obtained in the 24 hours prior to first dose.

⁴ Safety laboratory tests include WBC with differential, hemoglobin, platelets, creatinine, total bilirubin, ALT, AST, and INR.

⁵ Any laboratory tests performed as part of routine clinical care within the specified visit window can be used. Window during the 10 days of dosing is ± 1 day.

⁶ In-person visits are preferred but recognizing quarantine and other factors may limit the subject's ability to return to the site for the visit. In this case, the visit may be performed by phone.

- If still hospitalized at Day 15 and 29 or returns to the site for an in-person visit: assess adverse events, collect clinical data (ordinal and NEWS), vital signs, safety laboratory tests, and research laboratory samples (OP swab and blood) as able.
- If phone call only on Days 15 and 29 and all Day 22 visits: assess adverse events, clinical status (ordinal scale), readmission to a hospital, and mortality only.

⁷ Oropharyngeal swabs are preferred, but if these are not obtainable, saliva or nasopharyngeal or nasal swabs may be substituted.

⁸ To include markers of inflammation and coagulation: CRP, ferritin, fibrinogen, d-dimer, troponin.

[figure not shown]
⁹ Day 22 visit performed by phone.

¹⁰ Only collected at selected sites capable of collecting PBMC.

*See SOA in Appendices for study product-specific assessments.

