8.1.2.2 Ordinal Scale

The ordinal scale is the primary measure of clinical outcome.

The scale used in this study is as follows:

1. Not hospitalized, no limitations on activities;
2. Not hospitalized, limitation on activities and/or requiring home oxygen*;
3. Hospitalized, not requiring supplemental oxygen* - no longer requires ongoing medical care;
4. Hospitalized, not requiring supplemental oxygen* - requiring ongoing medical care (COVID-19 related or otherwise);
5. Hospitalized, requiring supplemental oxygen*;
6. Hospitalized, on non-invasive ventilation or high flow oxygen devices;
7. Hospitalized, on invasive mechanical ventilation or ECMO;
8. Death.

*For subjects on chronic supplemental oxygen, this pertains to an increased oxygen requirement above baseline.

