9. STATISTICAL CONSIDERATIONS

This is an adaptive platform study is intended to allow for several adaptations: 1) stopping enrollment into arms based on interim analyses of futility and efficacy and 2) addition of new experimental arm(s) into one stage, or 3) addition of separate study stages.

BET is a proof of concept study with the intent of identifying promising treatments that warrant future studies. Estimates produced from BET will also provide an improved basis for designing the future trials, in terms of sample size and endpoint selection. While the primary endpoint is Day 8 ordinal score, there is strong interest in analyses of secondary endpoints in assessing promise. The trial will enroll 100 patients per intervention and this will be compared with 100 control patients. Futility and early efficacy will be assessed after approximately 50 patients have been enrolled in the treatment and control arms. The interim analysis will find an intervention futile if its point estimate for the primary endpoint has an odds ratio <1 . An intervention can be declared efficacious early after 50 patients per arm if two-sided $p < .001$. If the intervention continues to 100 patients, it will be declared promising if the final two-sided p -value is $< .20$ and

will be considered as statistically significant if the final two-sided p-value < .05. Details of the statistical plan will be described in the statistical analysis plan (SAP).

Addition of new experimental therapies: If additional experimental arms are added, the sample size per arm will remain at 100. Analyses of newly added arm(s) will be performed comparing concurrently enrolled control subjects. This principle is used in general, that is, patients on interventions will only be compared to control patients who could potentially have been randomized to that intervention (i.e., they met eligibility criteria for the intervention and are at a site where the intervention was enrolling at the time of the patient's randomization.)

Statistical Hypotheses

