9.3 Statistical Analyses

9.3.1 General Approach

This is a proof of concept double-blind placebo controlled randomized trial testing a superiority hypothesis where interventions with a two-sided p-value < .20 will be declared promising, and will be considered statistically significant if the final two-sided p-value is < .05. Both 95% and 80% confidence intervals will be computed for the treatment effect corresponding to the primary and key secondary endpoints. One key secondary hypothesis will be highlighted for each individual intervention in the corresponding appendix. All endpoints will also be described according to the appropriate summary statistics (e.g., proportions for categorical data, means with 95% confidence intervals for continuous data, median for time-to-event data).

A statistical analysis plan will be developed and filed with the study sponsor prior to unblinding of study and database lock.

Unblinding of the study will occur after all subjects enrolled have reached the end of study, the study visits are monitored, and data is cleaned.

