9.3.3 Analysis of the Secondary Endpoint(s)

- 1) A stratified log-rank test of time to recovery will be performed, where stratification is according to baseline planned steroid use and severity. A supplemental analysis will also adjust for emerging COVID-19 treatments. Deaths will be considered censored at Day 29. If analyses are done prior to Day 29 for all patients (i.e., there is administrative censoring), then the Fine-Grey approach could be used for censoring deaths.
- 2) Differences in time-to-event endpoints (e.g., time to at least a one category improvement in ordinal scale) by treatment will be summarized with Kaplan-Meier curves and 95% confidence bounds. The same procedure will be used to compare time to at least a two-category improvement. Deaths will be considered censored at Day 29.
- 3) Change in ordinal scale at specific time points will be summarized by proportions (e.g., proportion who have a 1-, 2-, 3-, or 4-point improvement or 1-, 2-, 3-, or 4-point worsening).
- 4) Ordinal Score at Day 15 and Day 28; analogous to Day 8 analysis.
- 5) Duration of event (e.g., duration of mechanical ventilation) will be summarized according to median days with quartiles.
- 6) Binary data (e.g., incidence of new oxygen use) will be summarized as a percent with 95% confidence intervals. Comparisons between arms will be presented as differences in proportions with 95% confidence intervals.
- 7) Categorical data (e.g., 28-day mortality, ordinal scale by day or NEWS) may be summarized according to proportions by category and/or odds ratios with confidence intervals.

Procedures for handling missing data, including informative censoring (e.g., a missing duration of oxygen use endpoint due to a death), will be described in the SAP.

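### A subject discharged alive to hospice or end-of-life care counts as recovered under the literal definition, and the Day 29 rule for deaths does not reach that subject

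*Protocol*

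**What the plan says.** The key secondary objective in Table 1 (Synopsis, Section 1.1) is time to recovery: "Day of recovery is defined as the first day on which the subject satisfies 1 of the following 3 categories from the ordinal scale". The three categories are 1, 2 and 3 of the 8-point scale. Category 2 in Section 8.1.2.2 reads "Not hospitalized, limitation on activities and/or requiring home oxygen". Categories 1 and 2 are the only ones open to a living subject outside hospital. Neither carries a condition on discharge destination or prognosis.

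Section 9.3.3 sets the analysis, "A stratified log-rank test of time to recovery will be performed", and the handling of deaths, "Deaths will be considered censored at Day 29". The same censoring rule is given for time to improvement by one or two categories.

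An other secondary endpoint in Table 1 also turns on discharge: "Time to discharge or to a NEWS of ≤ 2 and maintained for 24 hours, whichever occurs first". After discharge, a phone visit under the Schedule of Assessments will "assess adverse events, clinical status (ordinal scale), readmission to a hospital, and mortality only". Readmission and death are thus collected, but the recovery definition uses neither.

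**The concern.** The scale runs from best (1) to worst (8), and Section 9.3.3 intends that a subject who dies is carried to Day 29 as not recovered. A subject sent out of hospital to die meets the recovery definition on the day of discharge. From then on the subject has had the event, and a later death cannot turn it into a censored non-recovery. The same subject is a success for recovery, improvement and time to discharge, and a death in 29-day mortality.

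If such discharges were more frequent in one arm, time to recovery would be biased in favour of that arm. This matters in a small trial with a lenient threshold. The design is "The trial will enroll 100 patients per intervention and this will be compared with 100 control patients", and "interventions with a two-sided p-value < .20 will be declared promising". Section 9 also says that secondary endpoints will weigh in judging promise.

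**Working it through.** **1. The rules applied to two subjects.** Both start in category 6 and both die after Day 8 and before Day 29. Subject X dies in hospital without a day in categories 1 to 3. Subject Y is discharged home for end-of-life care on Day 7.

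| Endpoint | X, dies in hospital | Y, discharged Day 7, then dies |
|---|---|---|
| Time to recovery | no event, censored at Day 29 | event on Day 7 |
| Improvement from baseline | none | 6 − 2 = 4 categories on Day 7 |
| Discharge or NEWS endpoint | no discharge event | discharge event on Day 7 |
| Day 8 ordinal score | in-hospital category | 2 |
| 29-day mortality | death | death |

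Across baseline categories 4 to 7, the apparent improvement is 4 − 2 = 2 up to 7 − 2 = 5 categories. Category 2 holds 34.6% of the expected control distribution in Table 5. Section 8.1.2.1 next schedules clinical status after an early discharge on Day 15, so Y's Day 8 score presumably follows from being alive and out of hospital. That last step is an inference.

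**2. The plan's own figures.** The protocol states no power or error rate for time to recovery. The nearest figure is Table 6 for the Day 8 score at an odds ratio of 2: 0.913 at alpha .20 and 0.765 at alpha .05. The formula of Section 9.1, solved for power with n per arm, is Φ(ln OR · √[(n/6)(1 − Σp̄³)] − z). With n = 100 and the Table 5 distribution it gives 0.921 and 0.769 without an interim look. Simulation with the interim rules (100,000 replications, Wilcoxon statistic) gives 0.908 and 0.761, so Table 6 is reproduced. The present point does not depend on it.

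**3. Frequency.** The protocol gives no hospice rate. Section 2.1 puts mortality in hospitalized patients above 7%. Assume that 10% to 30% of deaths follow an end-of-life discharge. Then 7% × 10% = 0.7 and 7% × 30% = 2.1 false recoveries per 100 subjects.

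**4. Effect on the log-rank test.** This is an illustration with no true treatment effect. All rates are assumptions:
- 100 subjects per arm; 75% truly recover in each arm.
- 12% in each arm either die in hospital or go to hospice, so the arms differ only in the split between the two; the remaining 13% do not recover by Day 29.
- Recovery days are 1 plus the whole part of an exponential time with mean 9, capped at 28.
- Hospice discharge is uniform on Days 4 to 15.
- Unstratified log-rank z = (O − E)/√V, no interim look, 2,000 replications.

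The result is the proportion with z > 1.28 in favour of treatment, which is the favourable half of two-sided .20 (nominal 10%).

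| Hospice, control / treatment | Literal definition | Hospice as non-recovery to Day 29 | Mean events, literal / corrected |
|---|---|---|---|
| 0% / 0% | 0.095 | 0.095 | 149.8 / 149.8 |
| 2% / 2% | 0.106 | 0.109 | 154.3 / 150.2 |
| 5% / 5% | 0.108 | 0.104 | 159.8 / 149.7 |
| 2% / 6% | 0.248 | 0.093 | 158.1 / 150.1 |
| 0% / 5% | 0.286 | 0.092 | 155.0 / 149.9 |

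The simulation error near 0.10 is √(0.1 × 0.9 / 2000) = 0.007, so the equal-use rows do not differ from nominal in any way that matters. Equal use adds about 4 or 10 false events. Unequal use of 4 to 5 points raises the favourable rate to about 25% to 29%.

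**The case against.** The protocol never mentions hospice, so the classification is inferred from the category text. Section 8.1.2.1 records hospitalization without defining it, and an inpatient hospice bed might be coded as hospitalized. The manual of procedures and the CRFs are not shown, so a discharge-destination field may exist. This stands, and it limits the point to discharge out of hospital.

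Section 9.3.3 leaves missing data and informative censoring to the SAP. That does not answer the point. This subject is neither missing nor censored; the protocol's fixed definition records an event. It is true that a stage appendix may name a different key secondary endpoint.

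The deaths are not hidden. 14-day mortality, 29-day mortality and time to death are separate endpoints, and appearing in both a discharge and a mortality endpoint is not in itself a contradiction. This stands.

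The size is the weakest part. With equal use the error rate hardly moves. The imbalances of 4 to 5 points exceed the whole assumed range of 0.7 to 2.1 per 100, and the protocol gives no reason to expect one in a double-blind trial stratified by site and severity. Blinding would not, however, prevent an imbalance caused by the agent itself.

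Finally, the assessment schedule is kept similar to ACTT so that its endpoints can be evaluated, and a changed definition could cost comparability. Reporting both definitions meets this.

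**Conclusion.** The point holds as a misclassification built into a stated definition. A subject discharged alive, out of hospital, for end-of-life care is recovered, improved and discharged on that day, and scores 2 on the primary endpoint if alive on Day 8. The Day 29 rule does not reach that subject.

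Three stronger readings are tempting, and the documents support none of them:
- That the death rule never operates. It still covers every death that precedes a recovery day.
- That the trial's conclusions are biased as planned. With equal use between arms the effect is a few extra events and an unchanged error rate; bias needs an imbalance.
- That the Day 8 score is materially distorted. One such subject per 100 against 3.5% expected deaths is 1/3.5 = 29% of that count. The one subject is posited, the ratio compares two counts, and it shows no effect on the odds ratio or its p-value. A subject who has died by Day 8 scores 8 anyway.

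The 25% to 29% rates rest on assumed hospice shares and on applying the .20 threshold to time to recovery, whereas Section 9.1 evaluates it for the Day 8 score. They show direction and sensitivity and are not a forecast. The change is cheap and worth making.

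**What to change.** In Table 1 and Section 9.3.3, state that discharge to hospice or for end-of-life care is not recovery, improvement or a discharge event, and is analysed as deaths are, censored at Day 29. Say how an inpatient hospice bed is coded. Record discharge destination if the CRF does not already do so. Add a sensitivity analysis of the Day 8 score that places these subjects in the worst category. Report the literal definition as a supplementary analysis for comparability with ACTT.

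The cost is one sentence in each place, at most one CRF field, slightly fewer recovery events, one Day 8 sensitivity analysis and one supplementary analysis. The change concerns endpoint classification only and leaves patient care as it is.
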